11.5.8. Scheduled Follow-up Visits

After the index cryoablation procedure (treatment arm) or AAD initiation (control arm) is reported in the study database, the database will calculate the target dates and windows for each visit to the site. Should a subject miss a visit or the visit fall outside the pre-specified window, a study deviation must be reported and the original follow-up schedule maintained for subsequent visits.

Data analyses include follow-up visits, regardless of whether the visit occurs within the window. Therefore, a late visit is preferred over a missed visit but must be accompanied by a deviation. Follow-up visit windows are listed in Table 6 and are based on days post-index procedure or AAD initiation.

Table 6: Follow-up Visit Windows

| Occurrence/ Visit | Window (Calculated days post-procedure or AAD initiation) | |
|---|---|------------|
| | Window Start | Window End |
| Randomization | -30 days | Day 0 |
| Index Cryoablation Procedure/ AAD initiation | Day 0 | Day 0 |
| 1 month | 31 days | 51 days |
| 3 month | 91 days | 111 days |
| 6 month | 165 days | 195 days |
| 12 month | 365 days | 395 days |

The following activities will occur at the follow-up visits:

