11.5.8.4. Twelve month Office Visit

- Review medications
- Adverse event assessment
- Review symptoms suggestive of recurrent AF/AT/AFL
- Health care utilization assessment- collect information about hospitalizations or emergency department visits experienced by the subject since the last visit
- 12 lead ECG
- 24h continuous ECG monitoring with ambulatory monitoring equipment. The subject will be instructed to apply the continuous monitoring patches and complete the 24 hours of continuous monitoring within 7 days prior to the 12 month visit. It is recommended that the study personnel call the subject to remind them of this requirement. If the subject is not able to apply the device prior to the visit, it may be applied by study personnel at the 12 month visit.
- EQ-5D and AFEQT Questionnaires
- Collect the ambulatory monitoring equipment and return to Medtronic (or designee). If the subject did not perform the continuous monitoring prior to the 12 month visit, apply the device to the subject to complete 24 hour continuous monitoring. Give the subject instructions on how to return the equipment.
- Chest X-ray, including inspiration and expiration films, is required for subjects whose PNI was unresolved at the 6 month visit
- In the case of suspected PV stenosis, Magnetic Resonance Imaging (MRI) or Computerized Tomography Scanning (CT scan) is required. It is not required at this visit if it was already completed at an earlier visit and PV stenosis was confirmed.
- Inform the subject they have completed the study

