15.1.5. Analysis Methods

The probability of a subject achieving success at 12 months (365 days) will be estimated using Kaplan-Meier survival analysis. The standard error will be approximated using Greenwood's formula. A two-sided 95% log-log confidence interval for the probability will be constructed. A two-sided log rank test with $\alpha = 0.05$ will be used to assess whether the failure rate differs between treatment groups.

Day 0 is defined as either the day of the index cryoablation procedure or the day in which AAD drug therapy is initiated. For subjects with treatment failure, the survival date will be set to the date of the treatment failure. For subjects without treatment failure through 12 months, those subjects will be censored at the last study contact date recorded on a CRF, which may include the last study visit, the exit date, or death date. If a subject without a treatment failure is lost to follow-up, the censoring date will be set to the last recorded study visit date. If treatment failure occurs on the day of index treatment, survival time will be set to 0.5 days.

If an occurrence of documented AF/AT/AFL resulted from rhythm monitoring that was initiated at the 12-month visit, then the date of occurrence used in the Kaplan-Meier analysis will be the minimum of 365 days from the cryoballoon ablation procedure/date of AAD initiation or the actual date of occurrence. This allows counting of all AF/AT/ AFL events found at the 12-month follow-up, even if the follow-up occurred after 365 days post-ablation.

The survival curves from 0 to 12 months will be presented for both treatment arms.

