### 6.2.2.4. Analysis Methods

The probability of a subject achieving success at 12 months (365 days) will be estimated using Kaplan-Meier survival analysis. The standard error will be approximated using Greenwood's formula. A two-sided 95% log-log confidence interval for the probability will be constructed. A log rank test with  $\alpha = 0.05$  will be used to assess whether the failure rate differs between treatment groups.

Day 0 is defined as either the day of the index cryoablation procedure or the day in which AAD drug therapy is initiated. For subjects with treatment failure, the survival date will be set to the date of the treatment failure. For subjects without treatment failure through 12 months, those subjects will be censored at the last study contact date recorded on a CRF, which may include the last study visit, the exit date, or death date. If a subject without a treatment failure is lost to follow-up, the censoring date will be set to the last recorded study visit date. If treatment failure occurs on the day of index treatment, survival time will be set to 0.5 days.

If an occurrence of documented AF/AT/AFL resulted from rhythm monitoring that was initiated at the 12-month visit, then the date of occurrence used in the Kaplan-Meier analysis will be the minimum of 365

days from the cryoballoon ablation procedure/date of AAD initiation, or the actual date of occurrence. This allows counting of all AF/AT/ AFL events found at the 12-month follow-up, even if the follow-up occurred after 365 days post-ablation but still within the visit window. Events found at 12-month visits outside of the window will be censored at the previous follow-up and described in deviation listings.

The survival curves from 0 to 12 months will be presented for both treatment arms.

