### 6.2.3.4. Analysis Methods

The probability of a safety event within 12 months will be estimated using Kaplan-Meier survival analysis. Greenwood's formula will be used to approximate the standard error of the survival curve, and a two-sided log-log confidence interval at 12 months will be reported.

Day 0 is defined as the day of the index cryoablation procedure. For subjects with a safety event, the survival date will be set to the date of the safety event. For subjects without a safety event, censoring will occur at the last study contact date with a corresponding CRF (i.e., the last study visit, exit date or death). If a subject without a safety event is lost to follow-up they will be censored on the date of the last study visit.

Any subsequent ablations a subject may have after day 0 will not reset their survival time; the date of the index procedure will remain as day 0 for purposes of the primary safety analysis. Safety events related to repeat ablation procedures occurring up to 365 days after the index cryoablation date will be considered as having met criteria for the primary safety endpoint, and will be counted as failures for this analysis. Safety events only observed at 12-month follow-up visits that occur 365 - 395 days after the index ablation (i.e. are in the visit window) will also count as safety failures at one year. Like with the primary efficacy objective, safety events found at 12-month visits outside of the window (>395 days from index ablation) will not be counted in this endpoint, but will be described in AE listings.

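### SAP 6.2.2.4 makes censoring at an out-of-window 12-month visit depend on what the visit finds, and conflicts with the protocol's rule for the same subject

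*SAP*

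**What the plan says.** **SAP.** Section 6.2.2.4 dates AF/AT/AFL from monitoring started at the 12-month visit at the earlier of day 365 and the actual day, but only for a visit inside the window. For the rest: "Events found at 12-month visits outside of the window will be censored at the previous follow-up and described in deviation listings". The same section gives the rule for everyone else, with no window condition: "For subjects without treatment failure through 12 months, those subjects will be censored at the last study contact date recorded on a CRF".

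**Protocol.** Section 15.1.5 has the same dating rule without a window limit: "This allows counting of all AF/AT/ AFL events found at the 12-month follow-up, even if the follow-up occurred after 365 days post-ablation". Section 11.5.8 says "Data analyses include follow-up visits, regardless of whether the visit occurs within the window", and prefers a late visit to a missed one. Table 6 there sets the window ("12 month | 365 days | 395 days") and puts the 6-month visit at day 165-195.

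**What counts as outside the window.** The efficacy section does not define it. Only the safety section, SAP 6.2.3.4, supplies a boundary: "Like with the primary efficacy objective, safety events found at 12-month visits outside of the window (>395 days from index ablation".

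**Which recordings are back-dated.** Both documents limit back-dating to this condition: "If an occurrence of documented AF/AT/AFL resulted from rhythm monitoring that was initiated at the 12-month visit". By default, however, protocol 11.5.8.4 has the subject apply the patches at home and "complete the 24 hours of continuous monitoring within 7 days prior to the 12 month visit".

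**The concern.** Take two subjects who both attend on day 400. The one with a clean recording is censored on day 400 and is at risk through day 365. The one in AF loses the event and is normally censored around month 6. Nothing differs between them except the finding, so the Kaplan-Meier assumption of non-informative censoring is broken by the plan itself. Under the protocol the second subject is a failure at day 365.

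The day-365 Kaplan-Meier success rate is the reported primary efficacy estimate. If the conflict is left open until data are in, choosing between the two rules becomes a post hoc choice of that estimate.

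Two further gaps sit beside it:
- Read literally, the SAP sentence also covers a 12-month visit held before day 365, so AF documented within 12 months would be dropped.
- AF on the self-applied recording is not back-dated, although both documents state the aim of counting all AF found at the 12-month follow-up.

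**Working it through.** **The plan's own figure.** The SAP's rates (69.9% and 45.9%, two-sided alpha 0.05, 90% power) give n per arm = [1.960·√(2·0.579·0.421) + 1.2816·√(0.699·0.301 + 0.459·0.541)]² / 0.240² = 86.8, so 87 per arm and 174 in total. Dividing by 0.9 gives 194. This matches SAP 7.1; no sample size figure is in dispute.

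**Inputs.** Success rates from SAP 7.1. Arm sizes of 105 (210 randomized 1:1) and 94 (the protocol's analysable number after 10% attrition). Rounded failures f: 28 and 51 of 94; 32 and 57 of 105 (cryoablation, AAD). *Assumptions:* the other failures are spread evenly over day 91-364, successes are last seen on day 380, and the previous follow-up is on day 180.

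**Formulas for one late-found failure in an arm.** Let s = n − f, and let j be the other failures before day 180.
- Protocol rule (event at day 365): s/n
- SAP rule (censored at day 180): (n − j)/n × s/(n − j − 1)
- AF truly began after day 365 (event-free at day 365): (s + 1)/n

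| Arm | j | Protocol | SAP | Event-free | SAP minus protocol, points |
|---|---|---|---|---|---|
| Cryo, 94 | 9 | 66/94 = 0.7021 | 85/94 × 66/84 = 0.7105 | 67/94 = 0.7128 | +0.84 |
| AAD, 94 | 16 | 43/94 = 0.4574 | 78/94 × 43/77 = 0.4634 | 44/94 = 0.4681 | +0.59 |
| Cryo, 105 | 10 | 73/105 = 0.6952 | 95/105 × 73/94 = 0.7026 | 74/105 = 0.7048 | +0.74 |
| AAD, 105 | 18 | 48/105 = 0.4571 | 87/105 × 48/86 = 0.4625 | 49/105 = 0.4667 | +0.53 |

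Moving the previous follow-up over day 165-195 changes the last column by at most 0.03. Three such failures per arm give +2.5 and +1.8 points at 94, and +2.3 and +1.6 at 105.

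**If the AF began after day 365.** Both rules fall short of the event-free value. The SAP rule is too low by 0.23 (cryo) and 0.47 (AAD) at 94, or 0.21 and 0.42 at 105. The protocol rule is too low by 1/94 = 1.06 or 1/105 = 0.95 points in each arm.

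**Log-rank test.** On these data at 94 per arm, z is −3.386 (protocol) against −3.392 (SAP) with one case per arm, and −3.43 against −3.45 with three. In paired simulations (4,000 trials per setting, one to three cases in each arm), power changed by at most 0.15 points and at most 8 decisions changed.

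**Equal shares or unequal lateness.** Suppose, per 100 subjects, 8 cryoablation and 14 AAD failures are first found at the 12-month visit. The protocol-rule difference is 24.0 points. Under the SAP rule it becomes:
- 23.8 with 10% of visits late in both arms
- 25.2 with 30% late in cryoablation and 10% in AAD
- 22.0 with those shares reversed

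**Follow-up discarded.** 365 − 195 = 170 to 365 − 165 = 200 days, a period in which weekly transmissions are required (protocol Table 5, footnote 4).

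**Self-applied recording.** The 7 days before a visit lie wholly after day 365 when the visit day minus 7 exceeds 365, so from day 373. That is 395 − 373 + 1 = 23 of the 31 in-window days. AF kept at its actual date then misses the day-365 estimate (1.06 or 0.95 points each), but still enters the log-rank test with z unchanged.

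**The case against.** **The SAP may set such rules.** Protocol section 15 leaves data-handling rules to the SAP and asks for an amendment only when a principal feature changes. SAP 6.1.2 also points to section 6.2 for visit-window handling. This stands as to authority, but it does not make a finding-dependent rule sound.

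**AF first seen late may have begun late.** This is the strongest point. A subject with clean weekly transmissions who is first positive on day 450 may well have been AF-free at day 365, and uncapped dating would call that a failure. If so, the protocol rule errs by more than the SAP rule. Brief weekly recordings can miss paroxysmal AF, so onset stays uncertain. A cap on lateness is therefore defensible. Censoring back to month 6 is not, because it discards the intervening monitoring for positive subjects only.

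**The tipping-point analysis covers it.** In part. SAP 6.4.1 turns a censored cryoablation subject into a failure, which tests the direction that would flatter the device. It also makes a censored AAD subject event-free at day 365 despite documented AF, and it does not correct the reported estimate.

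**The effect is small.** The objective is decided by the log-rank test, which hardly moves with equal numbers of cases per arm. This stands, and it limits the weight of the point.

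**Dating a day-380 recording at day 380 is accurate.** True for a strict 365-day estimate. The self-applied recording is raised only because the documents say they want all AF found at the 12-month follow-up counted.

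**Conclusion.** The point holds as an internal conflict and a finding-dependent censoring rule, and it should be fixed before analysis. Relative to the protocol rule, each case adds about 0.84 or 0.59 points (94 per arm) or 0.74 or 0.53 (105 per arm) to 12-month success, under the assumed failure timing. The documents do not give the number of late visits, so no total is claimed.

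Three stronger readings are tempting and not supported:
- *That the rule overstates true success.* It does so relative to the protocol's dating. If the AF began after day 365, the SAP figure is too low and the protocol figure lower still.
- *That it tilts the test towards cryoablation.* The shift in the difference can go either way. One simulation under no true difference took rejection in favour of cryoablation from 0.023 to 0.043, but it assumed 30% late visits in that arm and none in the other, which nothing in the documents supports. With 10% late in both arms, two-sided rejection was 0.049 and 0.051.
- *That the change is undeclared.* The readable part of SAP 6.8 does not mention it, but that section is partly redacted, so this cannot be established.

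The boundary of day 395 comes only from the safety section. Until the efficacy text says so, visits before day 365 are caught as well.

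**What to change.** 1. In SAP 6.2.2.4, delete the sentence on events found outside the window and the clause before it that limits counting to in-window visits. Late AF and late clean visits then follow one rule, whatever is found.
2. By default use the protocol 15.1.5 dating. Pre-specify a sensitivity analysis that censors subjects first found in AF after day 395 and late event-free subjects alike, at day 365 or at the last rhythm recording (weekly transmissions included) on or before it. Making that the primary rule is equally defensible if the protocol is aligned.
3. State that AF found at a 12-month visit before day 365 counts at its actual date.
4. In both documents, extend the back-dating condition to the 24-hour recording self-applied in the 7 days before the visit.
5. In SAP 6.2.3.4, remove the opening comparison with the efficacy objective, which would no longer be true.

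Cost: SAP wording, a clarifying phrase in the protocol and one extra sensitivity run. Reported 12-month success may be slightly less favourable in both arms.

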### **6.2.2.5. Determination of Subjects for Analysis**

The mITT cohort will be used for this analysis.

### **6.2.3. Primary Safety Objective**

Demonstrate an acceptable safety profile of the cryoballoon ablation procedure as a first line therapy in a non-drug refractory paroxysmal AF population.

#### **6.2.3.1. Hypothesis**

The following hypothesis will be tested in a one-sided test with  $\alpha = 0.025$ :

$H_0: P_s \geq 12\%$

$H_a: P_s < 12\%$ ,

where  $P_s$  is the probability of a safety event in subjects from the cryoablation arm.

#### **6.2.3.2. Endpoint Definition**

A primary safety event is defined as a serious procedure-related or cryoablation system-related adverse event that includes any of the following:

- TIA within 7 days
- Cerebrovascular accident within 7 days
- Major bleeding that requires transfusion or results in a 20% or greater fall in hematocrit (HCT) within 7 days
- Development of a significant pericardial effusion within 30 days. A significant pericardial effusion is one that results in hemodynamic compromise, requires elective or urgent pericardiocentesis, or results in a 1-cm or more pericardial effusion as documented by echocardiography.
- Symptomatic PV stenosis within 12 months; accompanied by one of the following: 50%-70% reduction in area of the pulmonary vein, with symptoms not explained by other conditions; OR >70% reduction in area of the pulmonary vein
- MI within 7 days
- PNI unresolved at 12 months
- AE fistula within 12 months
- Major vascular complication that requires intervention, prolongs the hospital stay, or requires hospital admission (within 7 days).

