| | 
Recurrences of atrial arrhythmias during the AAD optimization/blanking periods will not be counted in the determination of the first clinical failure for the primary endpoint.
 
Within the AAD optimization period/post-ablation blanking period, recurrent arrhythmias can be managed with medications or cardioversions. Reablation will be considered a primary endpoint failure at all times, including during the 90 day post-ablation blanking period.
 
Acute procedural failure (treatment arm only) is defined as:
 
 a) Inability to isolate all accessible targeted pulmonary veins (assessed for entrance block and, where assessable, exit block) during the index ablation procedure. b) Left atrial non-PVI ablations including but not limited to, ablation of linear lesions c) Use of a non-study device in the left atrium. 
Primary Safety Endpoint:
 
The following adverse events will be counted towards the primary safety endpoint:
 
 • Transient Ischemic Attack (TIA) within 7 days • Cerebrovascular accident within 7 days • Major bleeding that requires transfusion or results in a 20% or greater fall in hematocrit (HCT) within 7 days • Development of a significant pericardial effusion within 30 days. A significant pericardial effusion is one that results in hemodynamic compromise, requires elective or urgent pericardiocentesis, or results in a 1-cm or more pericardial effusion as documented by echocardiography. • Symptomatic PV stenosis within 12 months; accompanied by one of the following: 50%-70% reduction in diameter of the pulmonary vein, with symptoms not explained by other conditions; OR >70% reduction in diameter of the pulmonary vein • MI within 7 days • PNI unresolved at 12 months • AE fistula within 12 months • Major vascular complication that requires intervention, prolongs the hospital stay, or requires hospital admission (within 7 days). |
| 
Secondary Endpoints
 | 
 1. The difference in composite scores from the AFEQT questionnaire taken at baseline and 12 month visits, and the difference in composite scores for the EQ-5D questionnaire taken at baseline and 12-month visits. 2. 12-month rates of cardiovascular HCU events, and 12-month rates of cardioversion (either electrical or pharmacological). |
|  |  |

| | |
|--|--|
| | 
[REDACTED]
 |

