5.1.4.2. Primary Safety Endpoint

The following adverse events will be counted towards the primary safety endpoint:

- TIA within 7 days
- Cerebrovascular accident within 7 days
- Major bleeding that requires transfusion or results in a 20% or greater fall in hematocrit (HCT) within 7 days
- Development of a significant pericardial effusion within 30 days. A significant pericardial effusion is one that results in hemodynamic compromise, requires elective or urgent pericardiocentesis, or results in a 1-cm or more pericardial effusion as documented by echocardiography.
- Symptomatic PV stenosis within 12 months; accompanied by one of the following: 50%-70% reduction in diameter of the pulmonary vein, with symptoms not explained by other conditions; OR >70% reduction in diameter of the pulmonary vein
- MI within 7 days
- PNI unresolved at 12 months
- Atrial-esophageal fistula within 12 months
- Major vascular complication that requires intervention, prolongs the hospital stay, or requires hospital admission (within 7 days).

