| Chest X-ray (treatment arm only) | If phrenic nerve injury is detected during the procedure, the subject will be evaluated with inspiration/expiration chest x-ray at PHD and all follow-up visits until resolved. | | | | | | | |
| MRI or CT Scan (treatment arm only) | Required only for subjects with suspected PV stenosis. | | | | | | | |

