13.2. Reporting of Adverse Events

For the purposes of this study, the following Adverse Events will be collected starting at the time the subject signs the Informed Consent Form through the duration of the subject's participation in the study:

- All procedure related AEs
- All cryoablation system related AEs
- All AAD related AEs
- All cardiovascular related AEs
- All Serious Adverse Events (SAEs), regardless of relatedness

Reporting of these events to Medtronic will occur on an Adverse Event (AE) Form, including a description of AE, date of onset of AE, date of awareness of site, treatment, resolution, assessment of both the seriousness and the relatedness to the investigational device.

Each AE must be recorded on a separate AE Form. Exceptions include:

- Documented pre-existing conditions are not considered AEs unless the nature or severity of the condition has worsened. Additionally, arrhythmia episodes that are not new or worsening conditions and for which no action is taken are not reportable as AEs.
- Unavoidable Adverse Events, listed in section 13.1 need not be reported unless the adverse event worsens or is present outside the stated timeframe post-procedure.
- Cardioversions (DC or Drug) for recurrent symptomatic atrial fibrillation and other atrial arrhythmias are not considered serious adverse events.

For any changes in status of a previously reported adverse event (i.e. change in actions taken, change in outcome, change in relatedness), an update to the original AE must be provided. All adverse events must be followed until the adverse event has been resolved, is unresolved with no further actions planned, the subject exits the study or until study closure, whichever occurs first.

In the event that a subject is exited from the study prior to study closure, all efforts should be made to continue following the subject until all unresolved procedure or cryoablation system related adverse events, as classified by the investigator, are resolved or they are unresolved with no further actions planned.

At the time of study exit, all adverse events with an outcome of "Unresolved, further actions or treatment planned" must be reviewed and an update to the original AE must be reported. At a minimum, if there are no changes to the description, relatedness, test and procedures or actions taken, the outcome must be updated to reflect "Unresolved at time of study closure."

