15.2.2. Endpoint Definition

A primary safety event is defined as a serious procedure-related or cryoablation system-related adverse event that includes any of the following:

- TIA within 7 days
- Cerebrovascular accident within 7 days
- Major bleeding that requires transfusion or results in a 20% or greater fall in hematocrit (HCT) within 7 days
- Development of a significant pericardial effusion within 30 days. A significant pericardial effusion is one that results in hemodynamic compromise, requires elective or urgent pericardiocentesis, or results in a 1-cm or more pericardial effusion as documented by echocardiography.
- Symptomatic PV stenosis within 12 months; accompanied by one of the following: 50%-75% reduction in diameter of the pulmonary vein, with symptoms not explained by other conditions; OR >75% reduction in diameter of the pulmonary vein
- MI within 7 days
- PNI unresolved at 12 months
- AE fistula within 12 months
- Major vascular complication that requires intervention, prolongs the hospital stay, or requires hospital admission (within 7 days).

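### The primary safety event has conflicting definitions: the protocol disagrees with itself on whether events must be serious and related, and the SAP measures pulmonary vein stenosis by area where the protocol uses diameter

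*SAP*

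**What the plan says.** **Which events count.** The protocol synopsis and protocol 5.1.4.2 introduce the list with "The following adverse events will be counted towards the primary safety endpoint" and add no condition. Protocol 15.2.2 and SAP 6.2.3.2 introduce the corresponding list with "A primary safety event is defined as a serious procedure-related or cryoablation system-related adverse event that includes any of the following".

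**PV stenosis.** There are three versions in current text:

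- Protocol synopsis and 5.1.4.2: "50%-70% reduction in diameter of the pulmonary vein, with symptoms not explained by other conditions; OR >70% reduction in diameter of the pulmonary vein".
- Protocol 15.2.2: "50%-75% reduction in diameter of the pulmonary vein, with symptoms not explained by other conditions; OR >75% reduction in diameter of the pulmonary vein".
- SAP 6.2.3.2: "50%-70% reduction in area of the pulmonary vein, with symptoms not explained by other conditions; OR >70% reduction in area of the pulmonary vein".

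The visible text of SAP 6.8 says that the PV stenosis criterion was altered, and it refers to area. The change it declares is from 75% to 70%, measured against protocol version 4. It does not mention diameter. SAP section 3 says the SAP is based on protocol version 6.0.

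**Decision rule.** Protocol 15.2.3 and SAP 6.2.3.3 regard the objective as met if the upper limit of the two-sided 95% interval is below 12%. SAP 6.2.3.4 specifies a Kaplan-Meier estimate with a log-log interval.

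**The concern.** Read literally, 5.1.4.2 counts a listed event whatever its seriousness or cause, while 15.2.2 and the SAP drop it if it is judged non-serious or unrelated. Such events can reach the database. Protocol 13.2 collects "All procedure related AEs", serious or not, and "All Serious Adverse Events (SAEs), regardless of relatedness". An effusion of 1 cm seen only on echocardiography meets the list with no stated intervention or admission. Phrenic nerve injury (PNI) detected at the procedure is "evaluated with inspiration/expiration chest x-ray at PHD and all follow-up visits until resolved" (protocol Table 5), so asymptomatic cases can be found, and whether one is serious is a matter of judgement.

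This is one of two primary objectives, and the secondary hypotheses are tested only if the primary objectives are met. Under protocol section 14 the CEC's classification is used for analysis and the CEC reviews the applicable definitions; the protocol contains more than one. A choice between them made after the data are known would be open to the charge that the favourable wording was picked.

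**Working it through.** **1. Passages side by side**

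| Place | Serious and related only? | PV measure | PV cutoffs |
|---|---|---|---|
| Protocol synopsis | no condition | diameter | 50–70%, >70% |
| Protocol 5.1.4.2 | no condition | diameter | 50–70%, >70% |
| Protocol 15.2.2 | yes | diameter | 50–75%, >75% |
| SAP 6.2.3.2 | yes | area | 50–70%, >70% |

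The two main differences work in opposite directions. The filter can only remove events. Area, at the same percentages, can only add PV stenosis events. The version 5.0 change log names the synopsis, 5.1.4.2 and 15.4.2.1 for the 75-to-70 edit and omits 15.2.2, so the 75% there looks like a missed edit.

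**2. The plan's own figure.** SAP 7.2 uses an exact one-sided binomial test with n = 94, goal 12% and true rate 4%, passing at 5 events or fewer. P(X ≤ 5 | 94, 0.12) = 0.0246 and P(X ≤ 5 | 94, 0.04) = 0.825. Both reproduce. 94/0.90 rounds up to 105 per arm, or 210 randomized. The sizing arithmetic is not the problem.

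**3. Pass/fail boundary under the planned analysis.** With no censoring, S = 1 − x/n, Greenwood variance of log S is v = x/[n(n − x)], and the upper limit for the event rate is 1 − S^exp(1.96·√v/|log S|).

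| Events | Upper limit | Verdict |
|---|---|---|
| 4/94 | 10.9% | pass |
| 5/94 | 12.3% | fail |
| 5/105 | 11.1% | pass |
| 6/105 | 12.3% | fail |

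The last passing count c is therefore 4 at n = 94 and 5 at n = 105. At a true rate of 4.0%, P(X = 4 | 94) = 0.198 and P(X = 5 | 105) = 0.167. In those cases one reclassified event reverses the verdict.

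**4. Filter: illustration only.** Assume that 4.0% is the rate with the filter, and that removing it adds events in a further fraction d of treated subjects. The verdicts differ with probability P(X ≤ c | n, 0.04) − P(X ≤ c | n, 0.04 + d). For example, at n = 94 and d = 1%: 0.677 − 0.491 = 0.185.

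| d (assumed) | n = 94 | n = 105 |
|---|---|---|
| 0% | 0% | 0% |
| 0.5% | 9% | 9% |
| 1% | 19% | 18% |
| 2% | 35% | 36% |

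**5. PV measure.** For a circular lumen, diameter loss = 1 − √(1 − area loss). Area losses of 50% and 70% equal diameter losses of 29% and 45%. The SAP's upper category thus begins below the protocol's lowest threshold of 50% diameter: a symptomatic stenosis at 46–49% diameter loss falls in the SAP's top category and in no protocol category. Protocol Table 15 gives a PV stenosis rate of 0.04% (0.01–0.10%). Expected events are 0.0004 × 94 = 0.038, or 0.0004 × 105 = 0.042. Putting d = 0.0004 into the formula of step 4 gives 0.7% at either n; d = 0.0010 gives 1.9% (n = 94) and 1.8% (n = 105).

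**6. Can a counting rule matter here?** SAP 7.2 reports 5/163 (3.1%) or 7/163 (4.3%) from earlier data, depending on how asymptomatic PNI was counted. That is a shift of two events. The SAP does not attribute it to the serious-and-related filter, so it shows only that counting rules can move this endpoint.

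**The case against.** The strongest reply is that the analysed definition is settled. Protocol 15.2.2 and SAP 6.2.3.2 use identical wording for the filter, and these are the statistical sections. The unqualified list in 5.1.4.2 can be read as a summary, with relatedness implied by an objective about the safety of the procedure. This makes it likely that the analysis would follow the filter. It does not remove the conflict: 5.1.4.2 is itself the endpoint section, states what will be counted, and is nowhere subordinated to 15.2.2.

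Second, the affected group is narrow. Items that require transfusion, intervention or admission would usually be serious, and PNI still unresolved at 12 months could meet the permanent-impairment limb of the serious adverse event definition in protocol 13.1. This stands. It leaves mainly an echo-only effusion, an isolated haematocrit fall, and PNI judged non-serious.

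Third, the CEC could assign seriousness and relatedness without knowing the endpoint wording, and the SAP rule could be applied afterwards. That is workable, but only once it is settled which rule applies.

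Fourth, the added rates are assumed, and 2% is half the planning rate; Table 15 gives 0.53% for effusion or tamponade of all kinds. The n = 94 boundary ignores partial follow-up from subjects who leave; with no censoring, 5 events pass from n = 97 (11.9%). Both points stand, which is why ranges are given at two sample sizes and no single figure is claimed.

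Fifth, the PV point is numerically negligible, and part of SAP 6.8 is redacted, so a fuller declaration of the change to area cannot be excluded. This also stands.

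**Conclusion.** The concern holds and should be fixed before analysis. That the texts conflict is certain; how much it matters in practice is not. The serious-and-related filter is the part that could decide the result, and only if the count falls near the boundary: a 17–20% chance of landing on the last passing value at a true 4.0% rate, and a 9–36% chance of opposite verdicts if the filter excludes events in 0.5–2% of treated subjects. These figures assume no censoring, the planned log-log limit, and a 4.0% rate with the filter; the documents give no value for the excluded fraction. The area/diameter mismatch changes the verdict with probability of about 0.7%, and under 2% at the upper limit of the cited rate. The 75% left in protocol 15.2.2 is a minor missed edit.

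**What to change.** Before analysis:

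- Reconcile the protocol synopsis, protocol 5.1.4.2, protocol 15.2.2 and SAP 6.2.3.2 to one event filter, one PV measure and one cutoff, confirmed by the sponsor. This review does not say which is right.
- If area is intended, declare the change from diameter in SAP 6.8, against protocol version 6.0.
- Before editing the 50–75% range in protocol 15.2.4, check whether it describes what the older studies left out.
- State in SAP 7.2 which rule for counting asymptomatic PNI the 4% planning rate assumes.
- Give the CEC the single agreed definition.

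The cost is aligned wording in the protocol and SAP and one instruction to the CEC. No new data or patients are needed.
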